PPH contributes to near-miss cases due to the serious illness that can occur as a consequence that includes adult respiratory distress syndrome, coagulopathy, shock, loss of fertility, and pituitary necrosis (Sheehan syndrome) ^(14, 27). If PPH is prevented this could contribute towards reduced hospital stay, avoidance of expensive interventions for intractable PPH (such as hysterectomies and the need for blood products) and conserve our already strained resources.

In the light of the above, this research attempts to assess the efficacy of TXA in preventing PPH after caesarean delivery in a large enough population to be adequately powered to add to the current body of evidence, in Southern Africa where no regional studies have been done to assess TXA in obstetric patients.

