1.2. PARTICIPANTS

The participants were women undergoing elective caesarean sections at Harare and Parirenyatwa Hospitals.

Inclusion criteria

- Pregnant woman with signed informed consent***
- Understand English and/or Shona
- Estimated gestational age of 38 weeks or more
- Requiring Elective Caesarean Section defined as caesarean section performed before onset of labour
- Live intrauterine foetus

***The study enrolled participants who met the inclusion criteria including minors. Consent was sought from legally authorized representatives such as the parent or guardian where possible. Where this was not possible the pregnant participants who were under the age of 18 were considered emancipated minors by them having assumed adult responsibilities (becoming a mother) before 18 years of age ⁽⁵⁰⁾.

Exclusion criteria

Women with the following characteristics were excluded from the study:

- Placental Abruptio

- Emergency caesarean section
- Current or previous history of significant disease including heart disease, liver, renal disorders
- Known coagulopathy or history of deep venous thrombosis and/or pulmonary embolism, or arterial thrombosis (angina pectoris, myocardial infarction, stroke)
- History of epilepsy or seizures
- Autoimmune disease
- Sickle cell disease
- Intrauterine foetal demise
- Eclampsia/HELLP syndrome
- Administration of anticoagulants – clexane or antiplatelet agents in the week before delivery

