1.3. STUDY SETTING

The trial was conducted at two tertiary institutions that are affiliated to the University of Zimbabwe. These serve as referral centres for 12 local authority clinics located in Harare as well as district and provincial hospitals in the surrounding provinces: Harare Central Hospital i.e. Harare Maternity Hospital (HMH) and Parirenyatwa Group of Hospitals i.e. Mbuya Nehanda Maternity Hospital (MNMH). Most of the patients understood at least one of either English or Shona languages.

Located in the Southerton suburb, HMH is the referral centre for pregnant women mainly from the southern and western suburbs of Harare. The unit has an Antenatal Ward (ANW), Labour Ward (LW), Early Labour Ward (ELW), Post Natal Ward A (PNA) for patients after vaginal delivery and Post Natal Ward B (PNB) for patients post caesarean delivery. Babies with complications are admitted in the Neonatal Unit (NNU).

The northern and eastern suburbs are served by MNMH which is located in Avondale suburb. The unit has an ANW, a LW, Post Caesarean Section Ward (PCW) and a Postnatal Ward (PNW). Ill babies are admitted in the Neonatal Intensive Care Unit (NICU).

There are five teams with 3 to 4 consultants each at MNMH and 5 teams at HMH each with 2 to 4 consultants. MNMH delivers a total of 535 pregnancies per month while HMH delivers 1,335. On average 60 elective and 250 emergency caesarean sections are done at HMH per month, while 80 elective and 210 caesarean deliveries on average are done at MNMH. Refer to C in **Error! Reference source not found..**

Elective caesarean sections are performed by Senior House Officers and Registrars (including the principal investigator) mainly, with some cases performed by Senior Resident Medical Officers (in their second year of internship) or Consultants (usually in cases that have complications or serious concurrent medical/obstetric indications).

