1.14.2. Secondary Outcomes

1. Incidence of PPH defined by blood loss equal to or exceeding 1000 ml following elective caesarean section

- Based on visual estimation

2. Estimated blood loss during caesarean section

- Based on visual estimate of blood loss and calculated estimates

3. Need for blood transfusion

- Mean or median number of units of red blood cells transfused up to day 2 postpartum

4. Use of additional uterotonicics (such as oxytocin infusion or prostaglandins)

- Number of participants who required additional uterotronics

5. Incidence of emergency surgical interventions for PPH up to day 2 post-surgery

6. Mean change in HCT up to day 2 post-surgery

- Difference between the HCT on the day before surgery and day 2 post-surgery

7. Mean peripartum change in haemoglobin up to day 2 post-surgery

- Difference between the haemoglobin on the day before surgery and at day 2 post-delivery

8. Duration of mother's hospital stay

9. TXA side effects

- number of participants with headache, anaphylaxis, nausea, diarrhoea, dizziness, fatigue, nasal sinus complaints, transient visual disturbances, abdominal pain, complaints of feeling faint, reported by anaesthetists and theatre staff [time frame: up to discharge from the recovery ward on day of surgery]
- number of participants with deep venous thrombosis, pulmonary embolism, myocardial infarction, or any thrombotic event confirmed by laboratory investigations up to day 2 post-surgery
- number of participants with seizures up to day 2 post-surgery
- number of participants with renal failure (defined by the need for dialysis) up to day 2 post-surgery
- number of participants with hypotension reported by anaesthetists and theatre staff [time frame: up to discharge from the recovery ward on day of surgery]
- Vital signs before surgery
 - Heart rate before surgery
 - Systolic BP before surgery
 - Diastolic BP before surgery

- Vital signs after placental delivery
 - Heart rate after delivery of the placenta
 - Systolic BP after delivery of the placenta
 - Diastolic BP after delivery of the placenta
- Post-caesarean delivery creatinine (mg/dL)
- Postoperative urea g/L
- Postoperative aspartate transaminase (IU/L)
- Postoperative alanine transaminase (IU/L)
- Postoperative total bilirubin (IU/L)

10. Neonatal outcomes

- Birth weight in grams determined on the date of delivery
- Apgar scores at 1 and 5 minutes on the date of delivery

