- Reason for admission to NNU/NICU [time frame: up to discharge from NNU/NICU]
- Number of neonates with neonatal jaundice determined clinically [time frame: up to discharge from NNU/NICU]
- Number of neonates with thromboembolic events determined clinically [time frame: up to discharge from NNU/NICU]
- Number of neonates who died [time frame: up to the day of discharge of the mother]

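### Neonatal deaths are counted only to the mother's discharge, while the neighbouring neonatal items run to NNU/NICU discharge, so deaths in the unit after she leaves are not counted

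*Combined protocol and SAP*

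**What the plan says.** Section 1.14.2 (Secondary Outcomes), item 10, lists the neonatal outcomes. Four of them carry a follow-up period that can extend beyond the day of birth. Death is one of these, and its count closes when the mother leaves hospital: "Number of neonates who died [time frame: up to the day of discharge of the mother". The other three close when the baby leaves the unit. The thromboembolic item, for example, is worded as "Number of neonates with thromboembolic events determined clinically [time frame: up to discharge from NNU/NICU", and the items on jaundice and on why a baby was admitted share that end point.

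Section 1.3 (Study Setting) describes the unit as separate from the maternal wards: the NNU at HMH, and at MNMH "Ill babies are admitted in the Neonatal Intensive Care Unit (NICU".

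The mother's stay is itself an outcome, item 8: "Duration of mother's hospital stay". Section 2.3 (Justification) suggests a direction for it: "If PPH is prevented this could contribute towards reduced hospital stay".

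The documents do not give a fixed day of neonatal follow-up, a fixed day of maternal discharge, a rule that a mother stays while her baby is in the unit, or a sensitivity analysis for deaths after she leaves.

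**The concern.** There are two problems, of unequal weight.

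**Missed deaths.** Take a baby admitted to the unit whose mother goes home on day 3 and who dies there on day 6. The reason for admission and any jaundice fall within the stated time frames, but the death does not. The study follows this baby to the end of the unit stay and leaves out the worst outcome. This needs no assumption about what TXA does to length of stay.

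**A window that ends at a post-randomisation event.** The closing date depends on maternal discharge, which TXA might affect. Staff who know the allocation might also affect it, since section 1.7 states that there is no blinding and section 1.6 puts a group sticker on the notes. If stays differed by arm, so would the time over which deaths are counted.

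The second research objective (section 2.4) concerns adverse effects of TXA. The drug is given before delivery, and section 3.16 has the DSMB assess safety data. An incomplete death count weakens the neonatal part of that assessment.

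**Working it through.** **1. The plan's own design figure.** Nothing is stated for neonatal death. The only design calculation is the sample size in section 1.4. With p1 = 0.021, p2 = 0.058, mean 0.0395 and the printed z values:

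[1.96·√(2 × 0.0395 × 0.9605) + 1.28·√(0.021 × 0.979 + 0.058 × 0.942)]² / 0.037² = 579.8

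With an unrounded z for 90% power the result is 581 per group, or 1,162 in total, as stated. Neonatal death does not enter this calculation, so changing its time frame leaves N unchanged.

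**2. The time frames side by side.**

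| Item | Count ends at | Death in unit on day 6, mother home on day 3 |
|---|---|---|
| Reason for admission | NNU/NICU discharge | admission recorded |
| Jaundice | NNU/NICU discharge | recorded if present |
| Thromboembolic events | NNU/NICU discharge | recorded if present |
| Death | mother's discharge | not counted |

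**3. How many deaths could be missed.** The documents give no maternal stay and no timing of deaths, so both are assumed here. Suppose every mother leaves at 3 days regardless of her baby's condition. With exponential time to death of mean m days, the share counted is 1 − exp(−3/m):

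- m = 1: 95%
- m = 3: 63%
- m = 7: 35%
- deaths uniform over 7 days: 3/7 = 43%

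The loss is smaller if mothers tend to stay while their babies are in the unit.

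**4. How far the window could differ by arm through PPH.** The planned rates differ by 0.058 − 0.021 = 0.037. If each PPH adds d days to the stay (d is assumed), the difference in mean stay is 0.037 × d:

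- d = 2: 0.074 days
- d = 3: 0.111 days
- d = 5: 0.185 days

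Against an assumed 3.5-day stay, the first and last are 0.074/3.5 = 2% and 0.185/3.5 = 5%. In reverse, a one-day gap in mean stay would need 1/0.037 = 27 hospital days saved per PPH prevented. A half-day gap would need 0.5/0.037 = 13.5 days.

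**5. How many deaths to expect.** No rate is given. At an assumed risk of 0.2% to 1%:

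- 506 recruited in the initial period: 506 × 0.002 = 1.0 to 506 × 0.01 = 5.1 deaths
- 1,162 planned: 2.3 to 11.6 deaths

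**The case against.** **The rule is the same in both arms.** This is true. A reader might infer that the definition itself builds in unequal observation, or that TXA-arm babies are watched for death for a day or half a day less, which would make TXA look materially safer. The documents do not support that. Windows differ only if stays differ, and no section quantifies an effect on stay. Through PPH prevention the planned rates imply a small gap (step 4). The direction is also open, because adverse effects of TXA could lengthen stay. What stands is that the window could differ by arm, including through unblinded discharge decisions, to which no size can be attached.

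**Mothers may stay until their babies leave the unit.** The documents neither say so nor exclude it. If they do stay, fewer deaths are missed, but the written definition still permits the omission.

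**Adverse events are reported separately.** Section 1.10 sends any adverse event to a regulatory form and states no time limit, and a DSMB sees safety data. This is a partial safeguard. The sentence does not name neonatal death, and it does not alter the outcome that will be tabulated by arm.

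**The outcome is rare and secondary.** Eligibility requires "Estimated gestational age of 38 weeks or more", a live fetus and an elective operation, so deaths will be few and the comparison has little power under any definition. Neonatal death also sits under item 10, apart from the TXA side effects in item 9, so it would be too much to say that the adverse-effects objective rests on it. But with perhaps one to five deaths among 506 births, leaving out one or two would noticeably change the safety report.

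**Conclusion.** The mismatch is certain from the text: death is the one neonatal item with an extended time frame that is not followed to NNU/NICU discharge, and no other section repairs this. The consequence is possible under-counting of deaths in the unit. Its size cannot be fixed from the documents. The 35% to 95% range for deaths counted rests on an assumed 3-day stay and assumed timings.

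Dependence on the mother's discharge is a secondary weakness. On the plan's own PPH rates it probably amounts to about 2% to 5% of the window, assuming 2 to 5 extra days per PPH and a 3.5-day stay. That does not support a claim of substantial bias in favour of TXA.

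This is a weakness in safety ascertainment. It touches neither the primary outcome nor the sample size.

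**What to change.** Redefine the time frame for neonatal death, in both arms, as running to the later of the mother's discharge and the baby's discharge from, or death in, NNU/NICU. State as a limitation that the window remains variable in length for babies never admitted, because it still closes with the mother's stay. A fixed period from birth would remove that dependence, but would need contact after discharge that the plan does not include.

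The document is written in the past tense, so data may already be collected. In that case, recover vital status at NNU/NICU discharge for every admitted baby in both arms, as far as records and linkage allow, and report deaths by arm on the existing and the revised definition. Check feasibility first. The unit records are not described, sections 1.12 and 3.18 say that no personal identifiers were used, and the one register described as pairing patient details with study number (section 1.9) is for dispensing TXA, so it covers one arm only. If recovery is incomplete, report by arm how many admitted babies have unknown status.

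The cost is one line of outcome wording, one extra field for admitted babies and some record checking. Follow-up to NNU/NICU discharge is already planned for the neighbouring items.

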3.15. DATA REPORTING

The study is reported according to the Consolidated Standards of Reporting Trials (CONSORT) which ensures that RCTs are reported in a standardized manner internationally and that all study participants are accounted for clearly and transparently⁽⁵⁵⁾.

3.16. INDEPENDENT DATA AND SAFETY MONITORING BOARD

An Independent Data and Safety Monitoring Board (DSMB) was established for the study comprising of 3 individuals: Professor [name] (Statistician), Dr [name] (Obstetrician & Gynaecologist), and Dr [name] (Obstetrician & Gynaecologist).

The DSMB was established to assess at intervals the progress of the clinical trial, the safety data, and the critical efficacy endpoints, and to recommend to the sponsors and researchers whether to continue, modify, or stop the trial. The DSMB reviewed the analysis prepared for this report.

3.17. STOPPING RULES / DISCONTINUATION CRITERIA

If at any stage during the trial the principal investigator, co-investigators (supervisors), DSMB, or ethical authorities were satisfied that having due regard to the initial risks, discomforts or other adverse effects caused to persons taking part in the trial, it was in the public interest to stop or suspend the trial, the trial would be stopped or suspended immediately. The DSMB or ethical authorities would notify the investigator in writing accordingly. Ethical authorities, as well as the hospital authorities, would be notified accordingly by the investigator.

3.18. ETHICAL CONSIDERATIONS

Approval to conduct the study and to use the hospital records of patients was sought and obtained from the following:

Table 1 Ethical approvals

Ethical Body	Approval Number
Harare Hospital Research and Ethics Committee	HCHEC 300817/61
Joint Research and Ethics Committee (JREC) at	JREC/239/17
Parirenyatwa Group of Hospitals	
Medical Research Council of Zimbabwe (MRCZ)	MRCZ/B/1386
Medicines Control Authority of Zimbabwe (MCAZ)	B/279/5/35/2018

Refer to **Error! Reference source not found..**

Participants were requested to provide written informed consent. Refer to **Error! Reference source not found.** and **Error! Reference source not found..** Participants were given full disclosure of the nature of the study, the risks, benefits and alternatives. They were given an opportunity to ask questions. No participant was coerced into participation. Participants were assured that no punitive implication or denial of service would be encountered if they did not agree to enter the trial and were permitted at any time to withdraw their participation. Women in the study were not given any material benefits.

The researcher liaised with the team managing the patient to continue the usual care even when the patient was not willing to enter or withdrew their participation. The patient was free to communicate with the researcher if they felt they did not get due treatment. The study used only coded numbers with no personal identifiers to ensure confidentiality.

3.19. TRIAL REGISTRATION

The trial was registered on clinicaltrials.gov NCT03463993.

